3.3	Primary efficacy analysis.....	20
3.3.1	Primary efficacy endpoint	20
3.3.2	Formal analysis	20
3.3.3	Multivariate analysis.....	21
3.3.4	Subgroup analysis.....	21
3.3.5	Sensitivity analysis	22
3.3.6	Exploratory analysis.....	22
3.4	Secondary efficacy analysis.....	23
3.4.1	Secondary endpoint part 1	23
3.4.2	Secondary endpoint part 2-a	24
3.4.3	Secondary endpoint part 2-b.....	24
3.4.4	Secondary endpoint part 2-c	24
3.4.5	Secondary endpoint part 2-d, part 2-e and part 2-g	24
3.4.6	Secondary endpoint part 2-f.....	25

3.4.7	Secondary endpoint and part 2-h.....	25
3.4.8	Secondary endpoint part 2-i	25
3.4.9	Secondary endpoints part 3	25
3.5	Safety analysis.....	26
3.5.1	General Safety analysis.....	26
3.5.2	Adverse event of special interest	26
4	Quality assurance	28
5	Bibliographic references.....	28

Signature page

Trial biostatisticians

Names:

[name]

Date:

October, 3rd 2023

[name]

October, 3rd 2023

Approved by:

Coordinating Investigator

Name: [name]

[figure not shown]
Date: October 3rd, 2023

Chair of the Trial Steering Committee

Name: [name]

Date: October 3rd, 2023

Coordinating Centre Representative

Name:

Date:

[name]

October, 3rd 2023

[name]

October, 3rd 2023

Abbreviations

ACE inhibitors: angiotensin-converting enzyme (ACE) inhibitors

AE: Adverse event

ARB: Angiotensin receptor blockers

Chronic ESRD: Chronic end-stage renal disease

CRF: Case report form

CV: Cardiovascular

HD: Haemodialysis

MACE: Major cardiovascular events

MI: Myocardial infarction

NSAID: Non-steroidal anti-inflammatory drug

SAE: Serious adverse event

ACS: Acute coronary syndrome

Introduction

The purpose of this detailed statistical analysis plan is to describe precisely and unambiguously the planned statistical analyses to be carried out on the study database to support the completion of the Clinical Study Report (CSR).

All planned analyses identified in the protocol and in this SAP will be performed only after the formal database lock. A blinded data review meeting will be held prior to the database lock and completion of the final analyses. In addition, no database may be locked, random code unblinded, or analyses completed until this SAP has been approved.

Key statistics and study results will be made available to the Steering Committee following the database lock and prior to completion of the final CSR.

Any post-hoc exploratory analyses completed to support the planned study analyses, which were not identified in this SAP, will be documented and reported in appendices to the CSR. Any results from these unplanned analyses will also be clearly identified in the text of the CSR.

1 Study rationale and objectives

Chronic kidney disease (CKD) is a public health priority. The latest European data show an incidence of end-stage renal disease (ESRD) requiring renal replacement therapy of 118 per million inhabitants/year, a prevalence of 630 per million. The unadjusted mortality rate is 29% at 2 years and 52% at 5 years. ESRD is associated with increased cardiovascular (CV) morbidity and mortality (2 to 10 times that of a population with normal renal function). Heart disease is the leading cause of mortality in patients on haemodialysis (HD) (42% of total mortality). Despite these alarming observations, this syndrome remains the poor relation of CV prevention. Very few treatments are evidence-based and CKD patients on HD are usually excluded from CV prevention trials. Aside from two positive studies among ESRD HD patients with heart failure and severely impaired left ventricular ejection fraction (stages III-IV) using renin angiotensin aldosterone system (RAAS) blockers (beta-blocker carvedilol, or a combination of angiotensin converting enzyme inhibitor (ACE-I) with an angiotensin II receptor antagonist (ARA-II) telmisartan), two morbidity-mortality studies developed by the CIC-P Nancy, the designer of the present project, and specifically including ESRD HD patients, have showed on the one hand that a statin had no effect and, on the other, that an ACE-I had a positive effect (undersized study, generating a trend of efficacy). Another study conducted in HD diabetics showed that another statin had no effect. These limited and inconclusive findings make further studies by the pharmaceutical industry unlikely in the coming years. In order to avoid that HD patients, often excluded from CV morbidity-mortality trials, remain without evidence-based therapeutic resources and continue to present unacceptable CV morbidity and mortality rates, institutionally-sponsored trials are needed. Our group has significant experience in morbidity-mortality trials in HD.

Clinical and experimental data suggest that RAAS blockade with ACE-I or ARA-II can limit atherosclerosis and CV morbidity and mortality, independently of blood pressure reduction, at least in subjects at high cardiovascular risk without severe renal impairment. In non-dialysed patients with heart failure, three international controlled trials showed a reduction in cardiovascular morbidity and mortality induced by aldosterone antagonists (spironolactone and eplerenone). Our group participated in the design, conducting and publication of these three studies. The beneficial effects of aldosterone antagonists involve cardiovascular remodelling, including collagen synthesis, as well as effects on endothelial and immune functions. A recent randomised controlled trial conducted in early-stage CKD showed that adding spironolactone to ACE-I or ARBs reduces left ventricular mass and arterial stiffness, both of which are independent predictors of cardiovascular events

in patients with ESRD. Most clinicians are reluctant to use aldosterone antagonists because of the risk of hyperkalaemia. However, recent studies have demonstrated the safety of spironolactone in anuric ESRD HD patients.

Our study aims to determine the safety and efficacy of spironolactone on the reduction of cardiovascular events among ESRD HD patients, in comparison to placebo.

1.1 Primary objective

The primary objective is to determine the effects of spironolactone in comparison to placebo on a composite endpoint combining cardiovascular events of interest (major cardiovascular events and cardiovascular death). The primary endpoint is the time to onset of the first adjudicated expanded MACE event, i.e.:

- non-fatal myocardial infarction (MI) acute coronary syndrome,
- hospitalisation for heart failure,
- non-fatal stroke,
- or CV death.

Whenever a first event occurred, blinding is maintained and treatment continued until the end of the trial, and the patient continued to be followed as per the protocol.

MACE and death events are adjudicated by an independent blinded clinical event adjudication committee. The procedures and event definitions are described in an adjudication charter.

1.2 Secondary objectives

Part1

Following a hierarchical strategy of statistical tests including the primary endpoint, the secondary objective is to determine the effects of spironolactone versus placebo on the composite win ratio endpoint of: 1. all-cause mortality; 2. time to cardiovascular event (hospitalisation for heart failure, or non-fatal myocardial infarction, or non-fatal acute coronary syndrome or stroke) at 2 years using the Finkelstein and Schoenfeld method.

Part2

Additional secondary objectives will be considered for hypothesis generation:

- a) mortality rate from non-CV causes
- b) the cumulative rates of the composite outcome of non-fatal primary outcome events (hospitalisation for heart failure or non-fatal MI or acute coronary syndrome or stroke) and occurrence of
 - i. All-cause death from any cause,
 - ii. CV death
 - iii. non-CV cause
- c) cardiovascular event-free survival: survival without non-fatal MI and acute coronary syndrome, hospitalisation for heart failure, non-fatal stroke, or resuscitated cardiac arrest
- d) incidence of procedures related to stenosis or thrombosis of the vascular access for HD
- e) incidence of coronary or peripheral revascularisation (including lower-limb amputations)

- f) blood pressure (pre- and post-dialysis) and its inter-visit variability [Rossignol P, Cridlig J, Lehert P, Kessler M, Zannad F. Visit-to-visit blood pressure variability is a strong predictor of cardiovascular events in hemodialysis: insights from FOSIDIAL. Hypertension. 2012 Aug; 60(2):339-46. doi: 10.1161/HYPERTENSIONAHA.111.190397. Epub 2012 Jul 9.]
- g) Occurrence of complete arrhythmia by atrial fibrillation.
- h) incidence of hyperkalaemia > 6 mmol/l;

The following objectives and ancillary studies will be analysed in dedicated SAP:

- i) *estimation of the effect of treatment on the quality of life of patients with this dual pathology: CKD in HD and established cardiovascular pathology,*

Part3: Ancillary studies

- j) *Creation of a biological collection for subsequent biomarker studies (serum and DNA libraries),*
- k) *Post-study, mortality and cardiovascular morbidity assessed 3, 5 and 10 years after the end of the double-blind follow-up period, by consulting national epidemiological registers.*

A health economics ancillary study will complete this project.

1.3 Experimental design and studied population

1.3.1 Study outline

This is a randomised, controlled, double-blind, multicentre, parallel-group trial. After an open-label run-in period of one month under 25 mg spironolactone every second day (administered in practice after the HD session, three times a week), patients was randomised (spironolactone vs. placebo), and undergo titration over one month, with a maximum single dose of 25 mg/day. A pre-specified algorithm for the management of the risk of incident hyperkalaemia was followed, including dose adjustments, temporary discontinuation of the study treatment, in addition to the usual dietary measures, and the use of chelating resins and low-potassium dialysis baths.

Serum potassium levels was measured at the beginning of each session (3 times per week) over 2 months, and thereafter according to the titration algorithm data (in addition to usual follow-up, including serum potassium monitoring every two weeks), and during each visit of the protocol. Patients was followed for 2 years on average.

A Steering Committee (chaired by the coordinator, and comprised of nephrologists, cardiologists, pharmacologists, a statistician methodologist), an Oversight Committee and a Critical Events Adjudication Committee was planned.

1.3.2 Pre-specified algorithm for treatment administration and dosage

The selected dosages were based on literature data: satisfactory tolerance particularly in terms of serum potassium in patients on haemodialysis, choice of dosages similar to those with proven efficacy in cardiac failure patients (RALES), but slightly lower in light of the kidney failure.

Spironolactone was initially be administered at a single dose of 25 mg every second day administered in practice after the dialysis session, three times a week. Serum potassium levels were measured 3 times per week after initialisation of the

treatment throughout the entire run-in period of one month. Patients were excluded prior to randomisation if serum potassium is greater than or equal to 5.5 mmol/l on two occasions during the run-in or on the day of randomisation.

After randomisation, the dose was increased to a single dose of 25 mg/day by controlling serum potassium 3 times a week for one month, and thereafter every 3 months, in addition to usual follow-up, which includes at minimum performing a plasma ionogram every two weeks. Changes in treatment dosage of the trial and related serum potassium levels was collected in the case report form, without the need of an additional visit.

Dose adjustments during the course of randomisation: according to a proven algorithm in the EPHESUS and EMPHASIS-HF studies.

DOSE TITRATION ALGORITHM The target dose is 25 mg/d	
Pre-dialysis Serum Potassium (K ⁺) (mmol/L),	Dose adjustment or maintenance
<5.0	Increase in dose (if target dose not reached): 
 • If the current dose is 25 mg every second day (administered in practice after the session, three times a week): increase to 25 mg/d.
5.0 – 5.4	CONTINUE WITH THE CURRENT DOSE (no adjustment)
≥5.5	
LOWERING OF THE DOSE:
 
 • If the current dose is 25 mg/day, reduce to 25 mg every second day (administered in practice after the session, three times a week) • If the current dose is 25 mg every second day (administered in practice after the session, three times a week), temporary suspension of the treatment 
 → retest serum potassium levels before the next dialysis and proceed as follows: 
 * If serum K⁺ <5.5, resume study treatment at a dose of 25 mg every second day (administered in practice after the session, three times a week) * If serum K⁺ ≥5.5, temporary suspension of study treatment and retest serum potassium before the next dialysis

In parallel, in the event of hyperkalaemia deemed clinically significant by the investigator, the latter will follow the usual care protocols from his/her centre (intensification of dietary measures, use of chelating resins and low-potassium dialysis baths).

1.3.3 Randomization and blinding

The randomisation list was centralised and generated by the Biostatistics department of the Hospices Civils de Lyon. Randomisation was stratified on the centre, to ensure a balanced distribution of confounding factors between arms and between centres. After the run-in period, investigators were need to connect to the CSOnline electronic case report form of the study and randomize their patients. Treatment was automatically assigned following the pre-established randomization list. The allocation ratio was 1:1 between the two groups.

Treatment vials were indistinguishable, therefore, this is double blinded study.

1.3.4 Sample size determination

Assuming the following conditions:

- An annual event probability of events of 0.18 in the placebo arm (corresponding to an incidence of 19.84 per 100 person-years)
- A 30% reduction of this annual event probability in the spironolactone arm (active treatment), hence a probability of 0.126 (corresponding to an incidence of 13.46 per 100 person-years)
- A statistical power of 80% ($\beta = 20\%$)
- A bilateral test with a type-1 error rate α of 5%
- A premature study discontinuation rate (early drop-out) of 10%

A total number of **750 randomised patients (375 per arm)** to follow over 2 years in average is required to analyse the treatment effect with an exponential survival model. Considering early drop-out of 10% before randomisation, **825 patients** should be included at run-in phase.

[figure not shown]
1.3.5 Chronological sequence

Eligible patients having signed the consent form participate in the one-month run-in phase after which they were randomised conditional to the absence of hyperkalaemia ≥ 5.5 mmol/l on two occasions or on the day of randomisation or of serious adverse events.

The included and randomised patients participate in the study for a duration of 2 years on average, the latter of which can be amended by the Steering Committee in light of the rate of event occurrences. The study was completed when the number of incidents necessary for attaining a sufficient power has been observed. Blinding was lifted only in the case of a serious adverse event in which care management may be modified according to the treatment received by the patient: spironolactone/placebo; patients were followed until the end of the study.

Figure 1: Scheme of the study

Figure 1: ALCHEMIST trial design

(*): dosage of 25 mg/eod; patients presenting blood potassium > 5.5 mmol/l on two occasions will be excluded before randomization;
 (**): maximum dosage of 25 mg/d; could be reduced or temporarily suspended if blood potassium is > 5.5 mmol/l;
 From V1 to V12: Other visits will be scheduled if blood potassium is > 5.5 mmol/l.

Summary table of visits.

	Visit 1 W-4	Visit 2 W-2	Visit 3 D0	Visit 4 W+2	Visit 5 W+4	Visit 6 à 13 M3 to M24
Verification of the selection criteria	x					
Verification of the inclusion/exclusion criteria						
Pregnancy test (if applicable)	x					
Information/Informed consent	x					
Physical examination	x	x	x	x	x	x
ECG	x					
Dispensing of medication	x		x		x	x
Self-questionnaires on quality of life	x					x (**)
Randomisation			x			
Blood potassium	3/week	3/week	3/week	3/week	x	x
Verification of compliance		x	x	x	x	x
Dosage increase		x	x	x	x	x
Dosage adjustment (if necessary)				x	x	x
Concomitant treatments	x					x
SAEs		x	x	x	x	x

(**) only at V6, V9, V13, V17 and V21

1.3.6 Studied population

The studied population is patients with end-stage renal disease (ESRD) requiring haemodialysis (HD) - ESRD HD patients.

Inclusion criteria:

1. Adult men and women (INCLU1)
2. On haemodialysis for at least 45 days for ESRD regardless of aetiology including diabetes (INCLU4)
3. Weekly frequency of dialysis sessions of at least 3 per week (INCLU5)
4. Patient with at least one of the following comorbidities,
 - cardiovascular abnormalities or CV risk factor: left ventricular hypertrophy defined as a left ventricular mass > 130 g/m² in men and 100 g/m² in women (echocardiography) (INCLU6) OR Cornell Index (RaVL + SV3) > 28 mm in man, > 20 mm in women (electrocardiogram) (INCLU7), OR left ventricular ejection fraction <40% (echocardiography) (INCLU12 if not missing else INCLU8); or QRS wide > 0.14 sec (INCLU9) OR Left branch block (electrocardiogram) (INCLU10) measured in the twelve months preceding the inclusion;
 - Diabetes (INCLU13);
 - History of CV disease: coronary artery disease (INCLU14), or Symptomatic lower limb peripheral artery disease (INCLU15), or Carotid or renal artery stenosis > 50% (INCLU16), or Stroke (INCLU17), or Hospitalisation for heart failure (INCLU18), or Atrial fibrillation (AF) (INCLU11), or Current oral anticoagulant therapy for AF

indication(INCLU20) , cardiac valve prosthesis (INCLU21) or CRP > 5 mg/l since the last 3 months in the absence of currently documented infectious or neoplastic disease(INCLU19)

5. Patient having given his or her free and informed written consent (INCLU2)
6. Patient affiliated with social security scheme (INCLU3)

Exclusion criteria:

1. History of hypersensitivity to spironolactone (EXCLU1)
2. Patients with galactose intolerance, Lapp lactase deficiency or glucose or galactose malabsorption syndrome (EXCLU1)
3. Hyperkalaemia > 5.5 mmol/l during the two weeks prior to inclusion, or history of unscheduled haemodialysis for hyperkalaemia in the last 6 months, or hospitalisation for hyperkalaemia in the last six months (EXCLU2)
4. Mandatory indication for a combination of ACE-I and sartan or renin inhibitor (each being authorised separately) (EXCLU3)
5. Concurrent therapy that cannot be stopped by another potassium-sparing diuretic, potassium supplementation, NSAIDs or Cox-2 inhibitors (EXCLU3)
6. Kidney transplantation scheduled within the year (EXCLU4)
7. Symptomatic interdialytic hypotension (EXCLU5)
8. Acute phase of systemic disease (EXCLU6)
9. Uncompensated hypothyroidism (EXCLU7),
10. Acute hyperthyroidism (EXCLU8)

Moderate abnormalities in thyroid function tests are very common in dialysis patients. Experience shows that the at-large interpretation of hormone assays or biomarkers is difficult. In order to confirm decompensation, extremely high (hypothyroidism) or truly collapsed (hyperthyroidism) TSH levels are needed, accompanied with highly disrupted T3 and T4 levels. Moreover, acute hyperthyroidism is accompanied by symptoms or complications.

11. Any prior or concomitant clinical condition compromising the inclusion, at the discretion of the investigator (EXCLU9)
12. Heart transplantation(EXCLU10)
13. Severe uncontrolled arrhythmia(EXCLU11)
14. Stroke within 3 months prior to inclusion(EXCLU12)
15. Acute coronary syndrome in the month preceding inclusion(EXCLU13)
16. Recent (1 month) or planned coronary revascularisation by angioplasty (EXCLU14)
17. Recent (3 months) or planned CV surgery, other than the vascular access for HD(EXCLU15)
18. Woman of childbearing age without effective contraceptive methods (i.e. in the absence of contraindication, use of an oestrogen-progestin or progestin contraceptive, contraception (oral, transdermal, or implant) or an intrauterine device or local contraception (condoms or spermicidal gels), or a history of tubal ligation, adnexectomy or hysterectomy) (EXCLU21)
19. Pregnancy, breastfeeding or planning a pregnancy within 2 years(EXCLU22)
20. Uncooperative patient or whose compliance to the dialysis treatment (frequency of sessions) or to the protocol is uncertain (including planned absence during the first two months of the study) (EXCLU16).
21. SBP > 200 mmHg and/or DBP > 110 mmHg(EXCLU17)

22. Inability to provide enlightened information to the subject (subject in emergency situation, subject with difficulties in comprehension, etc.) (EXCLU18)
23. Subject under judicial protection (EXCLU19)
24. Subject under guardianship or curatorship (EXCLU20)

1.3.7 Interim analysis

No formal efficacy interim analysis was planned.

Oversight Committee: three safety analyses were performed during the study period. These analyses were conducted after the obtaining and follow-up of at least one month of 1/4, 1/2 and 3/4 of the patients to be included. All relevant events and SAE were reported (no statistical test).

The Oversight Committee recommended the continuation of the study.

2 Analysis sets

Data of patients without informed consent in compliance with French law or patients who withdrew their consent to participate in the study and specifically requested that their data be removed from the database, will be removed from the analyses.

2.1 Run-in period population (run-in period)

All included patients entering the run-in period and taken at least one dose of spironolactone

2.2 Intent-to-treat population (ITT)

The intent-to-treat population is defined as all randomised patients irrespective of the received treatment, whether assessable or not).

The analyses will be performed as intent-to-treat, according to the treatment assigned by the randomisation scheme (unless specifically stated for some of the criteria).

2.3 Per-protocol population (PP)

The PP population includes all randomised patients who received the study treatment assigned by the randomisation scheme and who did not experience any major protocol deviation.

A list of patients to be excluded from the randomised patients to create the PP-efficacy population will be established and validated by the Steering Committee prior to database lock. A corresponding file will be prepared by the Coordinating centre, with the following items: Centre ID, Patient ID, reason for exclusion, and transferred with the final database.

The major protocol deviations considered are reported below:

- Patients who did not meet the inclusion or exclusion criteria
- Errors in treatment administration/allocation
- Spironolactone added on and reported during study visits
- Treatment withdrawn at randomisation visit (study treatment never administered)

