3.2.3 Administration of the study treatment

Run-in period

On the run-in period population, the duration of run-in treatment will be described overall according to usual descriptive statistics (cf. paragraph 3.1), considering the following definition:

Run-in treatment duration =Duration between first intake at visit V1 and last medication taken.

Study treatment period

Study treatment administration will be described on ITT and PP populations by treatment group according to usual descriptive statistics (cf. paragraph 3.1), considering the following definition:

Treatment total duration =Duration between intake at randomization and last medication taken

NB: The study drug dose was not collected in the eCRF at each visit, only adaptation of doses are available. These variables will be analysed later on.

The premature drug withdrawal, duration and reason will be also described on each population.

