3.3.1 Primary efficacy endpoint

The primary endpoint is the time from randomisation to the onset of the first adjudicated expanded MACE event: non-fatal myocardial infarction (MI), acute coronary syndrome (ACS), hospitalisation for heart failure, non-fatal stroke, or cardiovascular death. Events were adjudicated and confirmed by an independent clinical event adjudication committee.

The full available follow-up time is the duration until all events are observed. Patients are censored at the date of renal transplantation. Patients that have shown no event and no renal transplant are censored at the date of the last available follow-up status (end of study or death, whichever occurred first), if any.

For analysis of time to first event, data will be expressed as two variables:

- A binary variable indicating whether any of the events included in the primary endpoint occurred, or the patient was censored.
- An integer variable for the number of days from randomisation to the first occurrence of an event (start date of the event – randomisation date + 1), or for event-free patients, from randomisation to censoring (censoring date – randomisation date + 1).

censored	date
0 (event)	Start date of the event is the first between : - Date of cardiovascular death - Date of cardiovascular event
1 (no event)	Censoring date is the first, following this order, between: - Date of renal transplantation - Date of death if not cardiovascular cause - Date of end of study alive

NB: cf. Appendix 2 eCRF data to construct the primary endpoint (to independent reprogramming)

In the case where several events comprising the primary outcome occur on the same day, CV death is prioritised over non-fatal CV event for description purposes.

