3.4 Secondary efficacy analysis

Statistical analysis of the secondary endpoints will be performed on the Intent-to-treat population. Secondly, the same analyses will be repeated on the per-protocol population.

3.4.1 Secondary endpoint part 1

To handle the multiple testing, outcomes will be analyzed using a hierarchical testing procedure until the p-value equals or exceeds 0.05, the primary outcome being the most important outcome, followed by the secondary outcomes ranked according to the importance order shown in below. The secondary objective will be considered by comparing the effects of spironolactone to placebo on: Composite of (1) death from any cause and (2) time to CV non-fatal event (hospitalisation for heart failure or non-fatal MI or acute coronary syndrome or non-fatal stroke) both at 2 years.

A composite endpoint, Finkelstein-Schoenfeld z score [8], is based on a combination of 1) all-cause mortality and 2) time to CV non-fatal events, both at 2 years, assuming a hierarchy of the two endpoints. Each patient i is compared to each patient j of the clinical trial in a pairwise manner and assigned a score, u_{ij} , of -1, 1 or 0, depending on whether the outcome is unfavourable, favourable or indeterminate in the hierarchy of outcomes. Thus, if patient i died before patient j , the score is -1; if patient j died before i , the score is 1. If it cannot be determined which patient died first (e.g., because of equality or censoring), then the second outcome (time to CV event) is compared and assigned a value of 1 or -1 depending on whether patient i has a better outcome or not. When it cannot be determined whether a patient has a more favourable outcome than the other (equality or censor at 2 years), then the score is assigned a value of 0.

The Finkelstein-Schoenfeld z score is based on the sum of patient scores in the experimental arm, and this statistical test assesses significant differences on the composite endpoints.

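### The per-protocol set drops a patient for all follow-up when spironolactone is added later, so a primary event that came before the add-on is lost from the PP sensitivity analysis

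*SAP*

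**What the plan says.** SAP section 2.3 defines the PP set as randomised patients "who received the study treatment assigned by the randomisation scheme and who did not experience any major protocol deviation". Membership is therefore decided per patient, not per period of follow-up. Four major deviations are listed. Three concern eligibility, errors in administration or allocation, and drug never taken ("Treatment withdrawn at randomisation visit (study treatment never administered"). The fourth is "Spironolactone added on and reported during study visits". The exclusion list "will be established and validated by the Steering Committee prior to database lock".

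For the primary endpoint, section 3.3.1 says "Patients are censored at the date of renal transplantation". Its only other censoring points are non-cardiovascular death and end of study, and Appendix 2 programs the same rule. Neither mentions added spironolactone.

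Section 1.1 says of a first event: "Whenever a first event occurred, blinding is maintained and treatment continued until the end of the trial". Follow-up also continues.

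Section 3.3 makes ITT the main basis for the primary endpoint. PP is the first sensitivity analysis in section 3.3.5. For the secondary endpoints, section 3.4 says "Secondly, the same analyses will be repeated on the per-protocol population". The quality-of-life SAP (section 3) uses both sets.

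**The concern.** An add-on reported at a follow-up visit happens after randomisation, yet it decides whether the patient is in the PP set from day 0. Because follow-up goes on after a first event, an add-on that comes after the event can be reported and can trigger exclusion. Take a patient who is event-free for ten months, is then hospitalised for heart failure (a primary event) and is afterwards given spironolactone. That patient complied up to the event, but both the patient and the event disappear from PP.

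Selection into the set can then depend on the outcome that the set is used to analyse. Fixing the list before database lock, with the blinded data review planned in the Introduction, guards against selection by known arm. It does not guard against selection by outcome, because the dependence lies in the rule. What is at stake is how a difference or agreement between ITT and PP can be read. The primary conclusion is not at stake.

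**Working it through.** **1. How the rules combine.**
- Section 2.3: any listed deviation removes the whole patient, and the add-on line has no time limit and no restriction to add-ons before a first event.
- Section 1.1: treatment and follow-up continue after a first event, so a later add-on can be recorded.
- Section 3.3.1 and Appendix 2: no censoring at add-on, so no part of the patient's follow-up is kept.

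Together these remove an adjudicated event that came before the add-on.

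**2. The plan's own figures.** Inputs from section 1.3.4: annual event probability 0.18 (placebo) and 0.126 (spironolactone), 375 per arm, 2 years on average, 80% power, two-sided 5%.
- Rates: −ln(1 − 0.18) = 0.1985 and −ln(1 − 0.126) = 0.1347 per year. These agree with the stated 19.84 and 13.46 per 100 person-years up to rounding. HR = 0.1347/0.1985 = 0.679.
- Schoenfeld's formula gives 209 events. The mean 2-year probability is (0.3276 + 0.2361)/2 = 0.2819, so N = 742. An exponential-model formula gives 757. The stated 750 is reproduced.
- Expected events at 750, with full 2-year follow-up and no loss: 375 × (1 − 0.82²) = 122.85 and 375 × (1 − 0.874²) = 88.55, total 211.4.

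**3. Whole-patient removal.** If r patients with an event are removed from an arm with E expected events, the rate becomes −ln[1 − (E − r)/(375 − r)]/2. The values of r are assumptions, because the SAP gives none.

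| Removed (placebo v spironolactone) | Placebo rate | Spironolactone rate | HR |
|---|---|---|---|
| none | 0.1985 | 0.1347 | 0.679 |
| 10% of event patients in each arm (12.3 v 8.9) | 0.1818 | 0.1227 | 0.675 |
| 10 v 0 | 0.1849 | 0.1347 | 0.728 |
| 15 v 5 | 0.1780 | 0.1280 | 0.719 |

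For example, 10 v 0: placebo −ln(1 − 112.85/365)/2 = 0.1849, and 0.1347/0.1849 = 0.728.

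With equal shares, 12.3 + 8.9 ≈ 21 of 211 events are lost and both rates fall by 8% to 9%, but the HR hardly moves. The unequal cases correspond to 10/122.85 = 8.1% v 0%, and 15/122.85 = 12.2% v 5/88.55 = 5.6%.

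**4. Simulation** (exponential times, 375 per arm, 2 years, 4,000 runs per scenario; a share of event patients deleted as placebo/spironolactone).
- Design effect: 10%/10% gives HR 0.671 against 0.675 in ITT, with power about 78% against 80%. 10%/5% gives 0.706 and 20%/10% gives 0.744.
- True HR of 1: equal shares give HR 1.00 and about 5% rejections. 10%/5% gives 1.04 and 6.0%; 20%/10% gives 1.10 and 11.3%.

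If events before the add-on are counted, the ITT value of about 0.68 is recovered in this model, in which every deletion follows an event.

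**The case against.** **No decision rests on PP.** This stands. ITT is primary, PP is a supporting repeat, and section 2.5 has set sizes and major violations shown by arm, so unequal exclusion would be visible.

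**Event-triggered add-on may be rare.** This also stands. A reader might infer that primary events do lead to added spironolactone and are being deleted. The SAP does not say so. Its rationale (section 1) limits the benefit of aldosterone antagonists in heart failure to non-dialysed patients and says most clinicians are reluctant to use them. It gives neither a frequency nor a link to events. The rule allows the deletion; how often it happened is unknown.

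**Removal in proportion to events does not bias the HR.** Correct to within about 0.004 in the calculation above. A material shift needs unequal shares. Treatment is blinded (section 1.3.3) and the SAP gives no reason to expect them. The unequal cases in the table move the HR towards 1, but that direction is not assured: 0 v 10 gives −ln(1 − 78.55/365)/2 = 0.1212, and 0.1212/0.1985 = 0.61.

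**Early stoppers.** A reader might also infer that PP is defective because patients who stop study drug early stay in it. Only drug never taken is listed, and section 3.2.3 says "The premature drug withdrawal, duration and reason will be also described on each population", so early stoppers are expected within PP. But the SAP never states that PP is meant to show treatment as taken, and its titration algorithm (section 1.3.2) includes temporary suspension. Keeping early stoppers is a choice, not an error. It limits how PP may be described.

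**Conclusion.** The concern holds for the add-on line. As written, section 2.3 lets something that happens after a primary event erase that event from the PP sensitivity analysis of the primary endpoint. The same set is used for the PP repeats of the secondary endpoints and for quality of life. The ITT primary analysis is untouched.

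The size is not known from the SAP. With equal assumed removal of 10% of event patients per arm, the cost is about 21 of 211 events and lower event rates, with the HR still near 0.68. With assumed removal of 10 v 0 or 15 v 5, the HR is about 0.72 to 0.73. These figures assume exponential event times, a full 2 years of follow-up without loss, and add-ons that follow events. They do not show that the PP result is biased, only that the rule permits it.

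This is worth correcting because the correction is cheap, not because the main result is at risk.

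**What to change.** For the time-to-event PP analyses:
- Delete the add-on line in section 2.3 as a whole-patient exclusion. Keep ineligibility, allocation error and drug never taken as exclusions.
- Keep patients with added spironolactone from randomisation, and censor at the date it starts or, if that date is not recorded, at the visit where it is first reported. State that an adjudicated event on or before that date counts.
- Add this censoring date to the PP version of the derivation in Appendix 2.

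Censoring does not carry over directly to event counts, blood-pressure variability or the quality-of-life models. State separately how their PP repeats handle data after an add-on.

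Do not describe PP as the effect of treatment as taken, because early stoppers remain in it. An analysis that also censors at permanent stop of study drug is an optional extra, not a required correction. It would need a stated lag and could itself be informative.

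The cost is a few lines of SAP text and one derived date. The downside is that censoring at add-on may be informative if the drug is added to patients at higher risk, so the result stays a sensitivity analysis beside ITT.
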